## **PROTOCOL SUMMARY**

This document complies with requirements of the Declaration of Helsinki, International Harmonized Standards: EN ISO 14155-1 and ISO 14155-2:2003(E) and with 21 CFR Parts 50, 54, 56, and 812.

Title: Fecal Microbiota Transplantation National Registry

**Précis:** A national data registry of patients receiving fecal microbiota

transplantation (FMT) or other gut-related-microbiota products designed to prospectively assess short and long-term safety and

effectiveness

**Mission:** To expand knowledge and optimize practice in the

transplantation of fecal microbiota or other gut-related-

microbiota products.

**Goals:** To assess short-term and long-term safety

To assess effectiveness

To gather information on practice in North America.

To promote scientific investigation

To aid practitioners and sponsors in satisfying regulatory

requirements

10 years

**Population:** All patients receiving FMT or other gut-related-microbiota

products and the donors providing specimens for the enrolled patients' FMT. Patients will be enrolled regardless of race,

gender, ethnicity, or age.

**Number of Sites:** 75

**Number of Patients** 4,000

Subject

Participation
Duration:

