#### 4.1.1 Recipient Inclusion Criteria

- Ability to give informed consent
- Receiving FMT or other gut-related microbiota product within 90 days after providing consent
- Access to internet and/or [contact] Donor Inclusion

- Ability to give informed consent
- Providing stool sample for FMT

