## 4.2 Subject Exclusion Criteria

Incarceration

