## 6.2 Classification of Events

#### 6.2.1 Relatedness

The site Investigator will assess the relationship of SAEs to FMT, as related or not related, based on clinical judgment and using all available information, and may include consideration of the following factors:

- Possible alternative causes of the SAE, including the disease under treatment, pre-existing
  conditions, concomitant use of other drugs, and presence of environmental or genetic
  factors.
- The temporal association between FMT exposure and onset of the SAE.
- Whether the manifestations of the SAE are consistent with known actions or theoretical toxicity of FMT.

The causal relationship between FMT and the SAE will be assessed using one of the following categories.

- 1. Not Related:
  - Temporal relationship is lacking (e.g., the event occurred before FMT); or
  - Other causative factors explain the event (e.g. pre-existing condition, other concomitant treatment);
- 2. Possibly Related:
  - Positive temporal relationship (e.g., the event occurred within a reasonable time frame following FMT); and
  - The SAE is possibly explained by FMT and/or, and there is a lack of other causal factors.
- 3. Related:
  - Positive temporal relationship (e.g., the event occurred within a reasonable time frame following FMT); and
  - The SAE is more likely explained by FMT than by other causes.

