## B. Baseline Characteristics

- Donor (if known)
  - o Age
  - o Race/Ethnicity
  - o Gender
  - o Height
  - Weight
  - Donor medical conditions (check any which apply)
    - No significant medical or surgical history
    - BMI ≥30
    - Hypertension
    - Hyperlipidemia
    - Diabetes type II
    - Depression/anxiety
    - CAD
    - Cerebrovascular disease
    - Asthma
    - Other\_\_\_
- Recipient characteristics (baseline)
  - o Age
  - o Race/Ethnicity
  - Gender

- Height
- Weight
- Medical co-morbidities
  - Metabolic (hypertension, diabetes II, hyperlipidemia)
  - Autoimmune (hypothyroid, RA, SLE)
  - Asthma/Allergic-Atopic conditions
  - Cardiovascular
  - Neurological conditions (MS, Parkinson, Alzheimer's, autism)
  - Psychological (depression, anxiety, eating disorder)
  - IBS
  - IBD
  - Immunocompromised from medical condition or medication
  - Other
- Labs (glucose, cholesterol, HDL, LDL, triglycerides, ALT, alkaline phosphatase, bilirubin, albumin, BUN, creatinine)
- CDI baseline characteristics
  - Disease characteristics (pre-FMT)
    - Mild illness (recurrent)
    - Moderate (more severe but uncomplicated disease)
    - Severe
    - Severe complicated
  - Duration of *C. difficile* infection (weeks between initial diagnosis and FMT)
  - Number of CDI episodes
  - C. difficile strain
    - o Nap-1
    - Non Nap-A
    - o Unknown
  - Other treatments courses received (and number of courses of each, if known) for CDI prior to FMT
    - o Metronidazole
    - o Vancomycyin
    - o Vancomycin taper/pulse dose
    - o Fidaxomicin
    - o Nitazoxanide
    - o Rifaximin
    - o IVIG
    - o Saccharomyces. boulardii
    - o Lactobacillus GG
    - Other probiotic
    - o Other\_\_
  - Immediate Pre-FMT treatment(s)
    - Antisecretory therapy?
      - No
      - Yes
- H2 blocker
- Proton Pump inhibotor
- o Probiotics?
  - No
  - Yes

- list
- Antibiotics?
  - No
  - Yes
- Metronidazole
- Vancomycin
- Other
- o If yes, were antibiotics stopped? (yes/no)
- Number of days off antibiotics prior to FMT
- IBD Baseline characteristics
  - o Type of IBD
    - CD
    - UC
    - IBD-U
    - Pouchitis
  - Disease location/extent
    - Montreal classification for adults >18 y/o
    - Paris classification for children <18 y/o

  - IBD treatment pre-FMT
    - Antibiotics
      - IV
      - Oral
    - Probiotics
    - Diet
      - Type of diet
    - Mesalamine
      - Oral
      - Rectal
    - Thiopurines
    - Methotrexate
    - Steroids
      - Oral

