## **Supplement 4. FMT Effectiveness Outcomes**

## A. Clostridium Difficile Infection

- Post-FMT treatment(s)
  - o Probiotics?
    - No
    - Yes
      - list
  - Antibiotics?
    - No
    - Yes
      - Metronidazole
      - Vancomycin
      - Fidaxomicin
      - Other
  - Days post-FMT antibiotic stopped
- Cure (Resolution of diarrhea without need for further anti-CDI therapy)
  - Cured with single FMT
  - Cured with >1 FMT
- Failure/Recurrence
  - o How recurrence was diagnosed
    - Symptoms only
    - Stool testing only
    - Symptoms and +stool testing (EIA)
    - Symptoms and + stool testing (PCR)
  - Time of recurrence (weeks post-FMT)
- Antibiotics received post-FMT for treatment of other infections
  - Agent
  - o Indication
  - Months post-FMT

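### Patients with an earlier FMT are eligible, but no baseline item names prior FMT and the counting origin of single versus repeat cure is undefined, so first and repeat exposures cannot be reliably separated.

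*Protocol*

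**What the plan says.** **Entry.** The Protocol Summary defines the population as "All patients receiving FMT or other gut-related-microbiota" products, plus donors. Section 4.1.1 sets the exposure criterion as "Receiving FMT or other gut-related microbiota product within 90 days after providing consent". Section 4.2 has one exclusion: "Incarceration". None of these asks for a first FMT.

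**Baseline history.** For CDI, Supplement 3, part B, asks for "Other treatments courses received (and number of courses of each, if known) for CDI prior to FMT". It names metronidazole, vancomycin, vancomycin taper or pulse, fidaxomicin, nitazoxanide, rifaximin, IVIG, two specific probiotics and other probiotics, and ends in a free-text Other. For IBD, the list under "IBD treatment pre-FMT" runs from antibiotics to cyclosporin or tacrolimus and also ends in Other. Neither names FMT. The remaining indications in part A have no prior-treatment list.

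**Outcome.** Supplement 4, part A, separates "Cured with single FMT" from "Cured with >1 FMT". It does not say whether the count starts with the FMT that qualified the patient for the registry or with the first FMT the patient ever received.

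**Use.** Section 3.1 times follow-up from FMT, to 10 years. Section 8.3 plans comparisons of delivery methods, with regression and propensity scores built on the recipient covariates collected.

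**The concern.** A patient whose earlier FMT failed, at another centre or at the same site, enters like any other. Unless the site volunteers the history under Other, the record looks the same as that of an FMT-naive patient. Three uses of the data then suffer:

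- **Cure by number of FMTs.** One site may count FMTs given within the registry and another may count lifetime FMTs. Without a baseline item nobody can reconcile the two, and the single-FMT cure rate can mix first treatment with retreatment of known failures.
- **Delivery-method comparisons.** If the share with prior FMT differs between methods and prior FMT predicts failure, it is a confounder that has not been systematically collected.
- **Long-term safety, the primary objective.** For these patients the earlier donor exposure and its date are not on record, so latency and donor attribution of later events cannot be assigned.

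This is more than analysis detail that a statistical analysis plan could supply, because no plan can adjust for or stratify on a variable that was not collected.

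**Working it through.** **1. Can prior-FMT patients enter?** Yes. The population statement, Section 4.1.1 and Section 4.2, read together, contain no FMT-naive condition.

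**2. Is prior FMT captured elsewhere?** The only other repeat-FMT item is the delivery schedule in Supplement 1, part F (multiple dose, maintenance). That supplement is completed once per site at initiation, so it describes practice and is not a patient's history.

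**3. Which stated figures are affected?** None.

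- Zero events in 4,000 (Section 8.1): one-sided 95% upper bound 1 − 0.05^(1/4000) = 0.00075; the two-sided version, 1 − 0.025^(1/4000), is 0.00092. Both are below 0.001, so the statement reproduces.
- 5% of 4,000: the Wilson interval is 4.37% to 5.72%, matching the stated 4.4% to 5.7%.

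Both refer to patients undergoing FMT, first or repeat, and stand as written. If the bound were claimed for first exposures only, n would be 4,000 × (1 − f), with f the prior-FMT share:

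| f (assumed) | n | upper bound |
|---|---|---|
| 10% | 3,600 | 0.00083 |
| 20% | 3,200 | 0.00094 |
| 30% | 2,800 | 0.00107 |

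It would pass 1 in 1,000 only when f exceeds about 25%.

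**4. Illustration for the cure rate.** Inputs: 89% cure in naive patients, borrowed from the mean in Section 1.2; 70% to 80% cure in prior-FMT patients, assumed; f, assumed. Pooled cure = (1 − f) × 0.89 + f × p(prior). At f = 10%:

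- 0.90 × 0.89 + 0.10 × 0.80 = 0.881, a fall of 0.9 points
- 0.90 × 0.89 + 0.10 × 0.70 = 0.871, a fall of 1.9 points

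**5. Illustration for delivery methods.** Spurious difference in failure = (difference in prior-FMT share) × (0.89 − p(prior)):

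| Imbalance (assumed) | p(prior) = 0.80 | p(prior) = 0.70 |
|---|---|---|
| 10 points | 0.10 × 0.09 = 0.9 points | 0.10 × 0.19 = 1.9 points |
| 20 points | 0.20 × 0.09 = 1.8 points | 0.20 × 0.19 = 3.8 points |

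**6. Scale.** Take 2,000 per method, as in Section 8.1, and 11% failure (100% − 89%). The standard error of a difference is √(2 × 0.11 × 0.89 / 2000) = 0.0099, about 1 point. A 10-point imbalance therefore moves the estimate by roughly one to two standard errors under these assumptions.

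**The case against.** **Points that stand.**

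- A reader might infer that the plan analyses a repeat FMT as a first exposure, or that the single-FMT box must be ticked when a second FMT works. No passage says so. Supplement 4 offers both categories, and a site counting lifetime FMTs could tick the other one. The fault is an undefined count, which allows misclassification but does not prescribe it.
- A reader might also infer that Section 6.2.1 forces a condition arising between an earlier FMT and the registry FMT to be called unrelated, since its example is "Temporal relationship is lacking (e.g., the event occurred before FMT". That section covers SAEs only and rests on clinical judgment using all available information. Its example says before FMT, not before the registry's FMT. Disease present at enrolment would be baseline co-morbidity and would not normally be graded there. In Supplement 6, new diagnoses carry no relatedness field at all.
- The illustration rests on assumed inputs. The 89% comes from about 300 reported cases and is not stated to be single-FMT or FMT-naive. Nothing in the protocol shows that repeat recipients cluster by delivery method.
- The 3% versus 5% example in Section 8.1 is not a fair yardstick, because failure here starts near 11%. From there, 2,000 per group and 90% power detect about 3.4 points (11% versus 14.4%: 3.24 × √[(0.0979 + 0.1233)/2000]). Only the 3.8-point corner of the table exceeds that.

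**Points that do not answer the concern.** Section 5.1 says the listed elements may be collected, and the eCRF itself is not shown. Yet the same section says the list was meant to be broad and inclusive; it prompts for individual probiotics but not for prior FMT. The Other field is weak capture: it prompts for no date, method or donor, and a blank cannot be read as none.

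**Conclusion.** The concern holds as a gap in data capture and definition. Prior-FMT patients are eligible, their history is not systematically asked for, and the counting origin of single versus repeat cure is not fixed. A repeat FMT can therefore be misclassified as a first exposure. The registry cannot reliably adjust delivery-method comparisons for prior FMT, or assign latency and donor attribution of long-term events in these patients.

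Overall incidence per registry patient and the zero-event bound are unaffected. The size of any bias cannot be derived from the protocol, which gives neither the prior-FMT share nor cure after an earlier FMT. The 0.9 to 1.9 points for a 10-point imbalance are an illustration under the stated assumptions, not an estimate. This is a cheap improvement worth making early, because the history may be hard to recover years later.

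**What to change.** 1. **Supplement 3, part B.** Add a required item for every indication: *Prior FMT or gut-microbiota product: no / yes / unknown; if yes, number, dates of first and last, method, donor or product.*
2. **Supplement 4, part A.** State that the single and more-than-one categories count FMTs from the index registry FMT onward.
3. **Reporting.** Present single-FMT cure and the delivery-method comparisons by prior-FMT status, or adjusted for it. This can be placed in the statistical analysis plan once the item exists.

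Leave eligibility unchanged. Do not add an analysis that counts exposure from the first known FMT unless it uses delayed entry at enrolment. Patients had to survive to enrol, so the earlier person-time would otherwise be immortal.

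The cost is one more eCRF item, one definition, and a slightly smaller denominator for results restricted to FMT-naive patients. No patient is lost from the registry.

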## **Supplement 4. FMT Effectiveness Outcomes**

## A. Clostridium Difficile Infection

- Post-FMT treatment(s)
  - o Probiotics?
    - No
    - Yes
      - list
  - Antibiotics?
    - No
    - Yes
      - Metronidazole
      - Vancomycin
      - Fidaxomicin
      - Other
  - Days post-FMT antibiotic stopped
- Cure (Resolution of diarrhea without need for further anti-CDI therapy)
  - Cured with single FMT
  - Cured with >1 FMT
- Failure/Recurrence
  - o How recurrence was diagnosed
    - Symptoms only
    - Stool testing only
    - Symptoms and +stool testing (EIA)
    - Symptoms and + stool testing (PCR)
  - Time of recurrence (weeks post-FMT)
- Antibiotics received post-FMT for treatment of other infections
  - Agent
  - o Indication
  - Months post-FMT

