**FMT for the treatment of recurrent CDI**: Since approximately 2000, there has been an alarming increase in the incidence and severity of CDI. Cases of CDI nearly doubled from 98,000 in 1996 to 178,000 in 2003, and the unadjusted case-fatality rate increased from 1.2% in 2000 to 2.3% in 2004. It is estimated that 3 million cases of CDI occur each year, obligating annual excess hospital cost of 3.2 billion dollars. Equally concerning has been the increased incidence of communityassociated CDI which now is being reported in populations previously believed to be at low risk, including children, peripartum women, and healthy individuals without a history of antibiotic use. C. difficile recurrence is a common management problem and occurs in up to 20% of patients after initial treatment. Patients who experience one recurrence have a 40% risk of an additional recurrence and those with 2 or more episodes face a 60% risk of another episode. While the first recurrence is generally treated with a second course of metronidazole or vancomycin, current guidelines recommend a tapering course of oral vancomycin. Treatment options are limited for the significant number of patients who continue to experience additional CDI recurrences. Interventions that have been used, but with little or no data to support efficacy, include intravenous immunoglobulin, rifaximin, nitazoxanide, and probiotics. FMT is performed to restore the phylogenetic diversity of normal stool and the associated "colonization resistance" that enables normal intestinal flora to resist overgrowth of *C. difficile*. Numerous case reports and retrospective case series have demonstrated benefit of FMT in patients with severe or recurrent CDI with a mean cure rate of 89% for the approximately 300 cases reported in the world literature 14,32-41. A randomized controlled trial published in 2013 confirmed the high efficacy of FMT. Methods used to administer FMT include nasogastric and nasointestinal tubes, upper gastrointestinal (GI) tract endoscopy, retention enemas, sigmoidoscopy, and colonoscopy.

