      - Rectal
      - IV
    - Biologics
      - Anti-TNF
      - Anti-Integrin
      - Ustekinumab
      - Other
    - Cyclosporin or tacrolimus
    - Other
  - IBD history
    - Number of years since initial diagnosis
    - Bowel surgery (ever)
    - IBD-related hospitalizations (within 12 months prior to FMT)
  - Severity of IBD at time of FMT (quiescent, mild, moderate, severe)
  - Disease activity scores (if available)

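### CDI cure covers both resolved diarrhea and mere absence of relapse, and the registry does not list diarrhea status at FMT, which is needed to tell them apart

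*Protocol*

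**What the plan says.** Supplement 4A gives one favorable CDI outcome: "Cure (Resolution of diarrhea without need for further anti-CDI therapy". It is subdivided only by whether one or more FMTs were needed, and no assessment time is attached. A separate failure/recurrence item records how recurrence was diagnosed and "Time of recurrence (weeks post-FMT".

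The recipient criteria in Section 4.1.1 are ability to consent, "Receiving FMT or other gut-related microbiota product within 90 days after providing consent", and a means of contact. None asks for diarrhea or active CDI on the day of FMT.

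Supplement 3A allows refractory, recurrent and severe CDI as indications. Supplement 3B records anti-CDI antibiotics just before FMT, whether they were stopped, and "Number of days off antibiotics prior to FMT". Its pre-FMT disease classes start at "Mild illness (recurrent") and rise to severe complicated, with no class for a patient without symptoms. The IBD block of the same supplement does have one: "Severity of IBD at time of FMT (quiescent, mild, moderate, severe").

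Section 1.2 gives two background risks. The first is "Patients who experience one recurrence have a 40% risk of an additional recurrence". The second concerns a longer history of CDI, where the protocol states that "those with 2 or more episodes face a 60% risk of another episode".

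**The concern.** Resolution presupposes something to resolve. The baseline form foresees FMT given during or soon after anti-CDI antibiotics, so some recurrent-CDI recipients can be expected to arrive with diarrhea already controlled. They meet the symptom half of the definition on arrival, and the remaining half then asks only whether they relapsed. In a refractory or severe case with active diarrhea, the same label records a change in clinical state.

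Effectiveness is a secondary objective. Section 2.2.2 wants variation in outcome by method to guide standardization, and Sections 8.1 and 8.3 plan comparisons between delivery methods. Section 8.3 rests those comparisons on covariates that the registry collects. If the share of recipients already symptom-free differs between routes, cure can differ between routes without any difference in effect. A baseline state that was never recorded cannot be adjusted for later.

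**Working it through.** **The plan's own figure.** The protocol states no cure rate without FMT and no sample size for CDI cure, so there is none to reproduce. The recurrence risks are cited inputs and are taken as given.

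**Inputs**
- From Section 1.2: recurrence risk 0.40 after one recurrence, 0.60 with two or more episodes. No time horizon is given, and there is no figure for refractory or severe CDI.
- Assumed, because the protocol neither gives nor collects it: the share *s* of CDI recipients who have recurrent CDI and are symptom-free at FMT.
- Assumed: the no-effect success rate *p_active* among recipients with active diarrhea.

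**Step 1. No-effect success in symptom-free recurrent CDI.** *p_free* = 1 − recurrence risk.
- One recurrence: 1 − 0.40 = 0.60
- Two or more episodes: 1 − 0.60 = 0.40

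At an early report such as 1 month the figure would be higher wherever relapses are still to come, but the protocol gives no timing from which to calculate this.

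**Step 2. What these recipients add to an overall CDI cure rate, if one were reported.** Contribution = *s* × *p_free*.

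| Assumed *s* | × 0.40 | × 0.60 |
|---|---|---|
| 25% | 10 points | 15 points |
| 50% | 20 points | 30 points |
| 75% | 30 points | 45 points |
| 100% | 40 points | 60 points |

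**Step 3. Confounding between two delivery routes with no true difference.** The no-effect success rate for a route is *s* × *p_free* + (1 − *s*) × *p_active*. Subtracting one route from the other gives

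(*s*₁ − *s*₂) × (*p_free* − *p_active*).

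With assumed shares of 90% and 50%, *s*₁ − *s*₂ = 0.40.

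| Assumed *p_active* | *p_free* = 0.40 | *p_free* = 0.60 |
|---|---|---|
| 0 | 0.40 × 0.40 = 16 points | 0.40 × 0.60 = 24 points |
| 0.20 | 0.40 × 0.20 = 8 points | 0.40 × 0.40 = 16 points |
| equal to *p_free* | 0 | 0 |

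The first row is the maximum for these shares, because it lets no active patient resolve without an FMT effect. The sign reverses if *p_active* exceeds *p_free*.

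**The case against.** The strongest reply is that this is a registry of all FMT recipients with safety as its primary objective, so open entry is deliberate and effectiveness is to be described, not tested. That stands. Nothing here argues for requiring diarrhea at entry, and the protocol plans no test of cure against a no-FMT rate.

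The registry also records indication, number of episodes, prior courses, current antibiotics and days off them, and Section 8.3 plans regression and propensity adjustment. These are useful but partial proxies: a patient on vancomycin may or may not have diarrhea.

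Section 5.1 calls the supplements elements that may be collected, so the live case report form could already hold the item. In that case only the outcome wording needs changing. Stratification and timing may also be set in an analysis plan that is not shown, but an analysis plan cannot supply a missing baseline field.

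A reader might infer three stronger things that the document does not support:
- **Symptom-free recipients are cured from day 0.** Only the diarrhea half is met then. The definition also requires no further anti-CDI therapy, provider reports begin at 1 month, and relapse has its own item.
- **The protocol pools both kinds of success into one rate.** The label is shared, but no section specifies a combined CDI cure rate.
- **40% to 60% of all CDI recipients would be cured without an FMT effect.** The figure applies only to symptom-free recipients with recurrent CDI.

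**Conclusion.** The point holds as a gap in outcome definition and data capture. One label carries two meanings, and the listed baseline data cannot separate them. Among symptom-free recurrent-CDI recipients, 40% (two or more episodes) to 60% (one recurrence) would count as cured with no FMT effect, taking the Section 1.2 risks at face value and without a time horizon. Their share of CDI recipients is unknown.

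The possible confounding between routes is conditional on assumptions. For shares of 90% and 50% it is at most 16 to 24 points, falls to 8 to 16 if 20% of active patients resolve with no effect, and vanishes if the two no-effect rates are equal. It would be wrong to read this as a demonstrated bias of that size.

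Nor does the 40% to 60% arise from the wording alone. It is background non-recurrence, present in any uncontrolled series, and better categories expose it without removing it.

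**What to change.** - Add one item to the CDI baseline block of Supplement 3B: diarrhea at FMT, yes or no.
- In Supplement 4A, record resolution of diarrhea for recipients with diarrhea at FMT and no recurrence for those without. Tie each to a named follow-up report.
- Report the two groups separately, and include the baseline item as a covariate in delivery-method comparisons.

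The cost is one field and revised outcome wording, with no added visit or test. The downside is that CDI success is reported in two smaller groups, each with a wider confidence interval than a single rate would have.
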